**Table 5: Assessment of Laboratory Adverse Event Severity**

HEMATOLOGY	Grade 1 (Mild)	Grade 2 (Moderate)	Grade 3 (Severe)
Hemoglobin Males	11.0 – 12.0 g/dL	9.5 – 10.9 g/dL	<9.5 g/dL
Females	10.3 – 11.3 g/dL	8.5 – 10.2 g/dL	<8.5 g/dL
Platelets	110,000 – 130,000/mm 	90,000 – 109,999/mm 	<90,000/mm 
WBCs (increase)	10,800 – 15,000/mm 	15,001 – 20,000/mm 	<20,000/mm 
WBCs (decrease)	2300 – 3200/mm 	1400 – 2299/mm 	<1400/mm 
ANC (decrease)	750 – 1000/mm 	500 – 749/mm 	<500/mm 
Absolute eosinophil count (increase)	700 – 1500/mm 	1501 – 5000/mm 	>5000/mm 
CLINICAL CHEMISTRIES	Grade 1	Grade 2	Grade 3
Serum creatinine	1.5 – 1.7 mg/dL	1.8 – 2.0 mg/dL	>2.0 mg/dL or requires dialysis
ALT Males	58 – 115 U/L	116 – 230 U/L	>230 U/L
Females	64 – 128 U/L	129 – 255 U/L	>255 U/L

### **9.2.5 Serious Adverse Events**

An SAE is an AE, whether considered related to a study product or not, meeting one of the following conditions:

1. Death during the period of protocol-defined surveillance
2. Life threatening: defined as an event that places a subject at immediate risk of death at the time of the event and does not refer to an event that hypothetically might have caused death were it more severe
3. Hospitalization during the period of protocol-defined surveillance: defined as at least an overnight stay in the hospital or emergency ward for treatment that would have been inappropriate if administered in the outpatient setting
4. Results in a congenital anomaly or birth defect
5. Results in a persistent or significant disability or incapacity: defined as a substantial disruption of the study subject's ability to carry out normal life functions
6. Any other important medical event that may not result in death, be life threatening, or require hospitalization, may be considered a serious AE when, based upon appropriate medical judgment, the event may jeopardize the subject and may require medical or surgical intervention to prevent one of the outcomes listed above.

### **9.2.6 Procedures to be Followed in the Event of Abnormal Laboratory Test Values or Abnormal Clinical Findings**

The Principal Investigator or appropriate co-investigator is responsible for reporting all AE/SAEs that are observed or reported during the study, regardless of the relationship to study products. AE/SAEs, abnormal clinical laboratory test values, or abnormal clinical findings will be documented, reported, and followed appropriately.

## **9.3 Reporting Procedures**

### **9.3.1 Serious Adverse Events**

AEs will be followed until resolution even if this extends beyond the study-reporting period. Resolution of an AE is defined as the return to pretreatment status or stabilization of the condition with the expectation that it will remain chronic.

All SAEs will be reviewed by a study physician, recorded on the appropriate SAE form, and followed through to resolution or stabilization by a study physician. All SAEs will be reported by email, telephone or fax within 24 hours of notification of the SAE occurrence to the Principal Investigator, via a scanned PDF version of an SAE form to:

### **9.3.2 Regulatory Reporting for Studies Conducted Under DMID-Sponsored IND**

Not Applicable

### **9.3.3 Regulatory Reporting for Studies Not Conducted Under DMID-Sponsored IND**

Following notification from the Principal Investigator, the IND sponsor (Baylor College of Medicine) will report events that are both serious and unexpected that are possibly, probably, or definitely related to the study product, to the FDA within the required timelines: fatal and life-threatening events within 7 calendar days (by phone, fax, or internet) and all other SAEs in writing within 15 calendar days. All SAEs not listed as possibly, probably, or definitely related will be reported to the FDA at least annually in a summary format.

All Adverse Events of Special Interest (AESIs; see below) will be reported to Sponsor, and FDA according to the same procedure as for reporting SAEs, and according to the same timelines as described above.

### **9.3.4 Adverse Events of Special Interest (AESI)**

Special attention will be paid to monitoring for the occurrence of certain adverse events termed, “**Adverse Events of Special Interest**” or AESIs. These include inflammatory and autoimmune disorders that may potentially be related to the use of an immunostimulatory adjuvant (although none have been associated with the use of Na-GST-1 in combination with either AP 10-701 or CpG 10104). The occurrence of the following AESI’s will be closely monitored:

- Neuroinflammatory disorders (optic neuritis, multiple sclerosis, demyelinating disease, transverse myelitis, Guillain-Barre syndrome, myasthenia gravis, encephalitis, neuritis, Bell’s palsy)
- Musculoskeletal disorders (systemic lupus erythematosus, cutaneous lupus, Sjogren’s syndrome, scleroderma, dermatomyositis, polymyositis, rheumatoid arthritis, juvenile rheumatoid arthritis, polymyalgia, rheumatica, reactive arthritis, psoriatic arthropathy, ankylosing spondylitis, spondylarthropathy)
- Gastrointestinal disorders (Crohn’s disease, ulcerative colitis, celiac disease)
- Metabolic diseases (autoimmune thyroiditis, Grave’s or Basedow’s disease, Hashimoto thyroiditis, insulin-dependent diabetes mellitus, Addison’s disease)
- Skin disorders (psoriasis, vitiligo, Raynaud’s phenomenon, erythema nodosum, autoimmune bullous skin diseases)
- Others (autoimmune hemolytic anemia, idiopathic thrombocytopenic purpura, antiphospholipid syndrome, temporal arteritis, Behcet’s syndrome, pernicious anemia, autoimmune hepatitis, primary biliary cirrhosis, primary sclerosing cholangitis, autoimmune glomerulonephritis, autoimmune uveitis, autoimmune cardiomyopathy, sarcoidosis, Stevens-Johnson syndrome).
- Vasculitides

In addition, disorders that may potentially be related to experimental hookworm infection will be defined as AESIs that will be closely monitored following CHHI, including:

- Gastrointestinal disorders (Crohn’s Disease, Ulcerative Colitis, Irritable Bowel Syndrome)
- Gastrointestinal bleeding
- Anemia (greater than Grade 1 low absolute hemoglobin concentration as defined in **Table 5**)
- Pneumonitis

The new onset of AESI’s during the study will be reported to the Sponsor, the DMID Medical Monitor, and the FDA in the same fashion as described above in **Section 9.3.1** for SAEs.

### **9.3.5 Medically-Attended Adverse Events (MAAEs)**

Special attention will be paid to recording medically-attended adverse events, which are defined as any clinical symptom or diagnosis (including local symptoms at the injection site or systemic

symptoms) for which medical evaluation and/or care is sought from a qualified healthcare professional, outside of a regularly scheduled study visit. Note that MAAEs are not the same as SAEs. Whether or not an AE is an MAAE will be recorded on the appropriate Case Report Form.

### **9.3.6 Reporting of Pregnancy**

Pregnancies occurring in study subjects will be reported on the study-specific Pregnancy Report form. No further study vaccinations or CHHI will be administered to pregnant subjects, but with the subject's permission all study mandated blood samples will be obtained and the subject will continue in follow-up for safety events. Efforts will be made to follow all pregnancies reported during the course of the study to pregnancy outcome pending the subject's permission. If a woman becomes pregnant after CHHI but before study Day 280, management of her infection will be followed as per **Section 7.7** of this protocol (i.e., deferral of treatment with albendazole until after the first trimester due to the uncertain risk of this medication during the first trimester).

## **9.4 Type and Duration of Follow-up of Subjects after Adverse Events**

AEs will be recorded if they start from the time of the first study vaccination (Day 0) up to 28 days after each dose of study vaccine, and from time of CHHI up to study Day 297 (to include the albendazole treatment period). AEs limited to AESI's and new-onset chronic medical conditions will be followed through approximately 6 months after the larval application (Day 380, approximately 10 months after the final vaccination).

SAEs will be followed from the time of the first study vaccination (Day 0 [Visit 1]) through resolution even if this extends beyond the study-reporting period (approximately 10 months after the third study vaccination [Day 380, Visit 39]). Resolution of an AE/SAE is defined as the return to pretreatment status or stabilization of the condition with the expectation that it will remain chronic.

Follow-up procedures, evaluations, and outcomes will be recorded on the appropriate data collection form.

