#### Safety

The following parameters will be evaluated for each formulation of Na-GST-1, in comparison to the saline placebo control:

1. Frequency of solicited injection site and systemic reactogenicity, graded by severity, on the day of each study vaccination through 14 days after each study vaccination.
2. Frequency of solicited adverse events, graded by severity, on the day of CHHI through study Day 280.
3. Frequency of study vaccine-related Serious Adverse Events from the time of the first study vaccination through approximately 10 months after the last study vaccination.
4. Frequency of clinical safety laboratory adverse events.
5. Frequency of unsolicited adverse events, graded by severity, from the time of each study vaccination through approximately 1 month after each study vaccination; and from the time of CHHI through treatment with albendazole (Day 297).
6. Frequency of new-onset chronic medical conditions through approximately 10 months after the third study vaccination.
7. Frequency of Adverse Events of Special Interest through approximately 10 months after the third study vaccination.

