## 9 ASSESSMENT OF SAFETY

### 9.1 Specification of Safety Parameters

Safety will be assessed by the frequency and severity of:

1. Study product (vaccine or CHHI)-related serious adverse events occurring from the time of the first study vaccination through approximately 10 months after the last study vaccination.
2. Study vaccine-related solicited Adverse Events – reactogenicity events occurring on the day of each study vaccination through 14 days after each study vaccination:
  - a) Injection site reactions including erythema (redness), induration (hardness)/swelling, pain, and tenderness.
  - b) Systemic reactions including fever, myalgia (body aches/muscular pain exclusive of the injection site), arthralgia (joint pain exclusive of the injection site), headache, nausea, and vomiting.
3. CHHI-related solicited adverse events – reactogenicity events occurring on the day of CHHI through study Day 280 (time of treatment with first dose of albendazole):
  - a) Application site reactions including pruritus, rash, induration (hardness)/swelling, pain, and tenderness.
  - b) Gastrointestinal reactions including abdominal pain, abdominal bloating, flatulence, nausea, vomiting, and diarrhea.
  - c) Respiratory reactions (possibly due to migration of larvae through the lungs) including cough and sore throat.
4. Clinical safety laboratory adverse events occurring throughout the study. Parameters to be evaluated include WBC, ANC, absolute eosinophil count, hemoglobin concentration, and platelet count; ALT; creatinine; rheumatoid factor; and, anti-ds DNA antibodies.
5. Unsolicited Adverse Events – non-serious adverse events occurring from the time of each study vaccination through approximately 28 days after each vaccination and from study Day 140 (day of CHHI) through Day 297.
6. New-onset chronic medical conditions occurring from the time of the first study vaccination through approximately 10 months after the last study vaccination.
7. Adverse Events of Special Interest occurring from the time of the first study vaccination through approximately 10 months after the last study vaccination.

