## 9.2 Methods and Timing for Assessing, Recording, and Analyzing Safety Parameters

### 9.2.1 Adverse Events

An adverse event (AE) includes any noxious, pathological or unintended change in anatomical, physiological or metabolic functions as indicated by physical signs, symptoms and/or laboratory-detected changes occurring in any phase of the clinical study, whether associated with the study product (i.e., vaccine, placebo or CHHI), and whether or not considered study product related. This includes an exacerbation of pre-existing conditions and intercurrent illnesses.

All AEs will be graded for severity and relationship to study vaccine or to CHHI. A licensed clinician (i.e. physician, nurse practitioner, physician assistant) listed on the Form FDA 1572 will be readily available for the duration of the trial to assess AEs. Should a subject call on a study clinician to report an AE, it will be fully documented in their study chart, and discussed with the Principal Investigator.

All AEs will be assessed by the investigator using the following protocol-defined grading system, as or described in **Tables 1-5**:

- Grade 1: **Mild** - No effect on activities of daily living; no medical intervention/therapy required
- Grade 2: **Moderate** - Partial limitation in activities of daily living (can complete  $\geq 50\%$  of baseline); no or minimal medical intervention/therapy required
- Grade 3: **Severe** - Activities of daily living limited to  $< 50\%$  of baseline; medical evaluation/therapy required

All AEs will have their possible relationship to study vaccine or CHHI assessed using the following terms:

- Definite: Clear-cut temporal association, and no other possible cause.
- Probable: Clear-cut temporal association and a potential alternative etiology is not apparent.
- Possible: Less clear temporal association; other etiologies also possible.
- Unlikely: Temporal association between the AE and the study product or the nature of the event is such that the study product is not likely to have had any reasonable association with the observed illness/event (cause and effect relationship improbable but not impossible).
- Not Related: The AE is completely independent of study product administration; and/or evidence exists that the event is definitely related to another etiology.

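### Protocol 9.4 stops general AE recording at onset Day 297, but 9.1 item 4 counts laboratory AEs, including RF and anti-dsDNA, throughout the study, and both are last tested at Day 320

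*Protocol*

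**What the plan says.** Protocol 9.4 is the recording rule, and it turns on onset: "AEs will be recorded if they start from the time of the first study vaccination (Day 0) up to 28 days after each dose". For the challenge phase the same sentence sets a fixed closing date: "and from time of CHHI up to study Day 297 (to include the albendazole treatment period"). Beyond that limit it lists exceptions. AESIs and "new-onset chronic medical conditions will be followed through approximately 6 months after the larval application", which 9.4 itself equates with Day 380, and SAEs have their own rule. Laboratory AEs are not among the exceptions.

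Protocol 9.1 treats laboratory AEs separately. Item 4 reads "Clinical safety laboratory adverse events occurring throughout the study", and its parameter list ends with RF and anti-dsDNA antibodies. The Day 297 limit appears in item 5, on unsolicited non-serious AEs, which are those "occurring from the time of each study vaccination through approximately 28 days after each vaccination" and then from Day 140 to Day 297.

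The primary safety outcomes in 3.2.1 have the same structure. Item 4, "Frequency of clinical safety laboratory adverse events", has no end date, while item 5 on unsolicited AEs stops at Day 297.

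RF and anti-dsDNA are drawn after baseline at Days 14, 56, 70, 112, 126 and 320 (Protocol 7.3 and Appendix A). The Day 380 visit has antibody assays to the vaccine antigen only.

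**The concern.** The last scheduled RF and anti-dsDNA test falls after the date on which 9.4 closes general AE recording. A subject first found positive at Day 320 has a laboratory AE under 9.1 item 4. Under 9.4 the same finding is recorded only if its onset is judged to be by Day 297, and with no test since Day 126 that cannot be established.

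The SAP table of laboratory AEs (5.7.5.1) is built by system organ class and preferred term, so it can count only findings entered as AEs. Relationship to study product is likewise assigned only to AEs (Protocol 9.2.1). SAP 5.7.5.6 also flags on the laboratory listing every abnormal value that meets the protocol's AE definition, and that definition has no Day 297 limit. One result could therefore be flagged as an AE on the listing and be absent from the AE table.

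These analytes matter here because Protocol 2.3.1.2 describes antibodies that may cross-react with DNA as a recognised concern with CpG adjuvants, and undertakes to monitor subjects closely for this laboratory evidence.

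**Working it through.** The plan gives no figure to reproduce. The check is of the schedule and of the rules side by side.

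**1. Which visits carry RF and anti-dsDNA.** The extracted schedule tables may have shifted columns, so the Appendix A blood volumes were used to confirm the text of 7.3. Volumes in mL: CBC 2, ALT/creatinine 5, RF/anti-dsDNA 5, antibody 10, cellular 50.
- Day 126: 2 + 5 + 5 + 10 + 50 = 72 (stated 72), so the test is included.
- Day 140: 2 + 5 + 10 + 50 = 67 (stated 67; it would be 72 with the test), so it is not included.
- Day 320: 10 + 5 = 15 (stated 15), so it is included.
- Day 380: 10 (stated 10), so it is not included.

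**2. Position of the last test against the cut-off.** Day 320 has a window of 14 days either side. The earliest draw is Day 320 − 14 = 306, which is after Day 297, so every on-schedule last test falls after the cut-off.

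**3. How the interval since the previous test divides.** The window after dose 3 nominally ends at Day 112 + 28 = 140, which is the day of CHHI, so recording is continuous from Day 112 to Day 297.
- Interval: 320 − 126 = 194 days.
- Inside the window: 297 − 126 = 171 days; 171/194 = 88.1%.
- After the cut-off: 320 − 297 = 23 days; 23/194 = 11.9%.
- Draw at Day 306: 9/180 = 5.0% outside. Draw at Day 334: 37/208 = 17.8% outside.

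These are shares of calendar time, not probabilities of onset.

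**4. Is there a rule for dating onset?** The SAP missing-data rules (5.1) impute partial calendar dates only. Nothing in either document dates the onset of an abnormality first seen at a scheduled draw.

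**5. Do the 9.4 exceptions catch it?** The AESI list in 9.3.4 consists of disorders, and isolated RF or anti-dsDNA positivity is not on it. Neither document says that isolated positivity is a new chronic condition.

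**6. What the other provisions say.**

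| Provision | Reading for a conversion first found at Day 320 |
|---|---|
| Protocol 9.4 | Recorded only if onset is by Day 297 |
| Protocol 9.1 item 4 | Counts |
| Protocol 9.2.1: "laboratory-detected changes occurring in any phase of the clinical study" | Counts |
| Protocol 9.2.6: investigator "responsible for reporting all AE/SAEs that are observed or reported during the study" | Counts |
| SAP 5.7.5.1: AEs to the last study procedure | Counts |

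**7. Scale of one omission, as an illustration only.** Neither document gives a seroconversion rate. With 12 per group, one unrecorded case would make that row of the laboratory-AE table 0/12 (exact 95% CI 0 to 26.5%) while the shift table shows 1/12 (8.3%, 0.2% to 38.5%).

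**The case against.** The strongest reply is that the documents largely settle the question. The windows in 9.4 closely match 9.1 item 5, so 9.4 can be read as the general rule for unsolicited AEs and item 4 as the specific rule for laboratory AEs. Protocol 9.2.1 and 9.2.6 and SAP 5.7.5.1 all point the same way. This stands as a reason to think most sites would record the event. It does not remove the conflict: 9.4 is worded for AEs in general, lists its own exceptions and omits laboratory AEs from them, and nothing says that 9.1 takes precedence.

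A reader might infer that a Day 320 conversion would be lost. The documents do not support that. SAP 5.7.5.6 tabulates shifts from baseline for both analytes and lists the values whether or not an AE is recorded. Protocol 11.4 (Primary Objective 2, analysis c) and SAP 5.7.4.1 report clinically significant values for individuals, with no Day 297 limit. Protocol 8.2.1 asks for clinically significant abnormal values to be repeated and followed up. Monitoring and data checks (Protocol 10.1 and 13) might also find a flagged value with no AE record, and the SMC reviews cumulative unblinded safety data at the end. Clinical autoimmune disease is collected as an AESI to Day 380.

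A reader might also infer that the pre-dose tests at Days 56 and 112 fall outside recording. That depends on reading the 28-day windows dose by dose, as 9.1 item 5 words them. The wording of 9.4 also allows one continuous window from Day 0, and then both tests are inside. A conversion at those visits has another route to action as well, because positive RF or anti-dsDNA is exclusion criterion 30 and loss of eligibility can stop later doses or the challenge (5.3.3).

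Finally, the manual of procedures and the eCRF are not available here and may contain a dating rule. That is possible, but it would not correct the protocol text.

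**Conclusion.** Protocol 9.4 is wrong as written: it is a recording rule inconsistent with 9.1 item 4. Severity is low. The possible loss is confined to the AE record, the relationship assessment and one count in the laboratory-AE table for a primary safety outcome. An omission can only lower that count. A reader might infer a bias between vaccine groups or an understated risk for the CpG group; the documents do not show which group would be affected, or that any case would occur.

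The conclusion rests on three assumptions: that at least one site user applies 9.4 as worded, that no dating rule exists outside the two documents, and that the Day 126 and Day 320 visits occur within their windows. It does not depend on the reading of Days 56 and 112. Nothing here touches the efficacy analysis.

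**What to change.** Add one sentence to Protocol 9.4: laboratory AEs as defined in 9.1 item 4, including new RF or anti-dsDNA positivity, are recorded by date of sample from the first dose through the last scheduled safety laboratory test (Day 320, Visit 38).

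Using the sample date removes the need to estimate onset and also settles the Day 56 and Day 112 pre-dose draws under either reading. No separate grading instruction is needed: Table 5 has no row for RF or anti-dsDNA, but the general three-grade scale in 9.2.1 already applies.

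The cost is a short amendment to the IRB under 15.6. It adds no test, visit or blood volume and needs no change to the SAP tables.

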## **9.5 Halting Rules**

If the study vaccine or CHHI is considered significantly reactogenic or results in significant AEs (see below and **Section 9.2**), additional vaccinations or CHHIs will be suspended until reviewed by the SMC, Independent Safety Monitor, DMID Medical Monitor, and IND sponsor (BCM). Any recommendation of the Independent Safety Monitor, DMID Medical Monitor, and SMC to resume or suspend further injections or CHHIs (either for an individual subject or the full study) will be communicated in writing to the sponsor and Principal Investigator. All communications from the SMC will subsequently be forwarded by the investigators to the IRB.

The following criteria will be used to define significant reactogenicity:

- One or more participants experience a protocol defined SAE that is determined to be possibly, probably, or definitely related to a study vaccine or CHHI, **OR**,
- One or more participants experience a protocol defined AESI that is determined to be possibly, probably, or definitely related to a study vaccine or CHHI, **OR**,
- One or more participants experience a protocol defined Grade 3 hypersensitivity reaction that is possibly, probably or definitely related to a study vaccine or CHHI, **OR**,
- Two or more participants experience a protocol defined Grade 2 hypersensitivity reaction that is probably or definitely related to a study vaccine or CHHI, **OR**,
- Three or more participants experience the same objective physical finding or laboratory abnormality of Grade 3 or higher (with the exception of isolated Grade 3 erythema or swelling at the site of vaccination or Grade 3 erythema and/or rash at the site of application of the larvae), that is determined to be probably or definitely related to a study vaccine or CHHI, **OR**,
- Three or more participants experience the same Grade 2 or higher safety laboratory abnormality (excluding eosinophilia [or increased white blood cell count secondary to eosinophilia] after CHHI) or Grade 3 clinical AE that is possibly, probably or definitely related to a study vaccine or CHHI.

